CMV reactivation: CMV DNA load >1000 cp/ml in serum as measured by polymerase chain reaction (PCR).

CMV disease: organ dysfunction (pneumonitis, enteritis, retinitis, encephalitis, hepatitis, and bone marrow suppression) due to CMV infection.

CMV reactivation treatment failure: persistent CMV DNA load of more than 1000 cp/ml or CMV disease after 2 weeks of adequate treatment with antiviral therapy or relapse of CMV DNA load of more than 1000 cp/ml within 4 weeks after adequate

treatment with antiviral therapy or contraindication for treatment with antiviral therapy at the discretion of the physician.

Complete response: Complete disappearance of CMV DNA load for at least 4 weeks.

Partial response: reduction of CMV DNA load of > 1 log but no complete disappearance of CMV DNA load for at least 2 weeks.

Stable disease: no significant change (<1 log) in viral DNA load and no complete disappearance of CMV DNA load for at least 4 weeks.

Progressive disease: persistent increase in CMV DNA load of > 1 log during 4 weeks or new CMV disease.

SUMMARY:

Treatment with CMV pp65-specific T cells generated by use of a CMV pp65 protein-spanning peptide pool in patients with CMV reactivation or CMV disease after allogeneic stem cell transplantation (alloSCT)

Objectives:

- To assess the feasibility, tolerability and safety of administration of donor derived CMV pp65-specific T cells in patients with CMV reactivation or CMV disease after alloSCT.
- To determine the presence of CMV-specific T cells at different time points after infusion of CMV pp65-specific T cells.
- To evaluate whether administration of CMV pp65-specific T cells in patients with persistent CMV reactivation or CMV disease after alloSCT leads to complete or partial responses.

Population:

- Recipients of alloSCT (age 0-75 years) with CMV reactivation who fail antiviral therapy (defined as **CMV reactivation treatment failure**: persistent CMV DNA load of more than 1000 cp/ml or CMV disease after 2 weeks of adequate treatment with antiviral therapy or relapse of CMV DNA load of more than 1000 cp/ml within 4 weeks after adequate treatment with antiviral therapy or contraindication for treatment with antiviral therapy at the discretion of the physician) **or**
- Patients who develop **CMV disease** (organ dysfunction (pneumonitis, enteritis, retinitis, encephalitis, hepatitis, and bone marrow suppression) due to CMV infection).
- Number of patients to be treated with CMV pp 65 specific T cells will be 15.

Inclusion criteria:

[figure not shown]
- age 0-75 years
- recipient of alloSCT for standard indication according to national- and European Group for blood and Marrow Transplantation-guidelines (see appendix D)
- Possibility to obtain PBMC by leukapheresis from the CMV seropositive donor or availability of peripheral blood stem cell graft (PBSCT) or of a CD34-negative subfraction of a CD34-positively selected PBSCT product of the donor prepared and cryopreserved at a GMP-facility or stem cell center.
- **CMV reactivation treatment failure** (persistent CMV DNA load of more than 1000 cp/ml or CMV disease after 2 weeks of adequate treatment with antiviral therapy or relapse of CMV DNA load of more than 1000 cp/ml within 4 weeks after adequate treatment with antiviral therapy or contraindication for treatment with antiviral therapy at the discretion of the physician) **or** **CMV disease** (organ dysfunction (pneumonitis, enteritis, retinitis, encephalitis, hepatitis, and bone marrow suppression) due to CMV infection).

- Written informed consent by the patient and/or parent(s) or legal guardian(s).

Exclusion criteria:

- Life expectation < 3 months.
- End stage irreversible multi-system organ failure.
- Pregnant or lactating women.
- Severe psychological disturbances.
- Patient HIV positive.
- Donor HIV positive.

Study design for treatment of CMV reactivation and/or CMV disease with allogeneic CMV pp65-specific T cells

Investigational product:

The CMV pp65-specific T cell product will be generated from PBMC from a donor leukapheresis product, from a peripheral blood stem cell graft (PBSCT material) or from a CD34-negative subfraction of a CD34 positively selected stem cell graft prepared and cryopreserved at a GMP-facility or stem cell center, whichever is available.

PBMC will be exposed to the CMV pp65-derived 15 mer peptide pool, after which CMV-pp65-specific T cells will start to produce Interferon gamma (IFN γ). After overnight incubation, IFN γ secreting T cells will be isolated using the CliniMACS® Cytokine Capture System. The positively isolated fraction will be washed, after which the percentage of IFN γ - and CD137-positive T cells will be determined. When $\geq 20\%$ of the T cells are IFN γ and/or CD137-positive the CMV pp65 T cell product will be released. The number of cells that will be infused in the patient will be determined by the number of non-specific T cells in the product. The maximal amount of non-specific T cells in the product is $< 0.3 \times 10^6/\text{kg}$ body weight in patients transplanted with related donors and $< 0.15 \times 10^6/\text{kg}$ body weight in case of unrelated donors. After release, the CMV-pp65-specific T cell product will be resuspended in a solution of NaCl 0,9%, supplemented with human albumin (2%), after which the product can be administered.

Investigational treatment:

CMV pp65-specific T cells are a cell therapy product that will be administered after alloSCT in case of CMV reactivation treatment failure or CMV disease. The CMV pp65-specific T cells will be derived from a CMV seropositive donor. The product will contain an aimed dose of $10\text{-}20 \times 10^6$ total T cells. This dose is based on the amount of cells we expect to isolate on the basis of the currently performed phase I/II clinical study (LUMC 2004-01) on the treatment of refractory CMV reactivation using CMV pp65-specific CD8+ T cells and preclinical data of the current strategy. All cells isolated will be infused if $\geq 20\%$ of the T cells are IFN γ and/or CD137 positive and the maximal amount of non-specific T cells in the product is $< 0.3 \times 10^6/\text{kg}$ body weight in patients transplanted with related donors and $< 0.15 \times 10^6/\text{kg}$ body weight in case of unrelated donors. If the number of non-specific T cells in the product exceeds these criteria, the infused dose will be adjusted accordingly. The cells will be administered intravenously at the department of Hematology of the LUMC. In case of ongoing CMV reactivation or CMV disease and no severe toxicity, the procedure may be repeated 2 times with at least 4 weeks interval.

Risk/benefit:

Potential benefit of participation to this study is a reduction of the CMV DNA load which may lead to a reduction of development of severe CMV disease or cure of CMV disease. A potential risk of participation to this study is development of acute GvHD.

Contraindications for administration of CMV pp65-specific T cells:

- Life expectation < 6 weeks.
- End stage irreversible multi-system organ failure.
- Acute GvHD overall grade \geq III.
- Treatment with corticosteroids in an equivalent dose of >0.5 mg/kg prednisone.
- No CMV reactivation or CMV disease.

Study endpoints:

- The number of events of acute GvHD, death and all other adverse events.
- The number of CMV-specific T cells at different time points after infusion of CMV pp65-specific T cells.
- The number of complete responses or partial responses of CMV reactivation or CMV disease after infusion of CMV pp65-specific T cells.

Follow-up:

Follow-up of patients will be performed until 6 months after last infusion of CMV pp65-specific T cells or until subsequent DLI, whichever comes first.

In adults:

Weeks after infusion	0	1	2	3	4	5	6	7	8	12	16	20	24
Infusion of cells	x				(x)				(x)				
History and PE	x	x	x	x	x	x	x	x	x	x	x	x	x
Blood	x	x	x	x	x	x	x	x	x	x	x	x	x
CMV DNA	xxx	x	x	x	x	x	x	x	x	x	x	x	x
CMV tetramer	xx	x	x	x	x	x	x	x	x	x	x	x	x
Chimerism							x			x			x
xxx day 0, 1, 2													
xx day 0, 1													

The volume of blood for quantification of CMV-specific T cells by tetramer staining and functional assays (intracellular cytokine staining) is 50 ml.

The volume of bone marrow for chimerism analysis is 10ml.

In children:

Sampling of blood will be according to study protocol “adoptive immunotherapy for adenovirus infections after allogeneic stem cell transplantation in children” as approved by the CCMO. PBMC samples (20ml) will be taken and stored at 2 week intervals for the investigation of the presence and function of CMV-specific T cells until 3 months after last infusion. Blood sampling for this specific protocol will be combined with blood sampling for regular monitoring of the transplantation as much as possible.

Interim analysis:

After the first 3, 6 and 10 patients an interim analysis will be performed by the principal investigator.

Premature termination of the study:

In case of increase of >1 point of overall grade acute GvHD in 2 out of the first 3 patients, or 3 out of the first 6 patients, or 4 out of the first 10 patients, the study will be closed temporarily for inclusions and the outcomes in all patients will be discussed in order to decide whether potential beneficial effects of the treatment could overcome non-beneficial effects of GvHD.

End of study:

End of the study is defined as 6 months after the infusion of CMV pp65-specific T cells of patient number 15 or at time of subsequent DLI of patient number 15.

1. INTRODUCTION AND RATIONALE

Patients with hematological diseases can be successfully treated with allogeneic stem cell transplantation (alloSCT). After transplantation, patients suffer from a prolonged period of immune deficiency resulting in an increased risk of opportunistic infections, including cytomegalovirus (CMV) reactivation. CMV reactivation after alloSCT can cause serious disease with high mortality in case of absence of CMV-specific T cells. Treatment with antiviral drugs is associated with myelosuppression and nephrotoxicity and CMV reactivation often relapses. Reconstitution of the CMV-specific T-cell repertoire directed against immunodominant proteins, like CMV pp65, in the first year after alloSCT has been demonstrated to confer sustained protection from CMV disease. Furthermore, for the long-term protection against CMV the development of CMV-specific T-cell immunity has been found to be essential. It has been demonstrated that adoptive transfer of donor derived CD8⁺ CMV-specific cytotoxic T lymphocytes can result in a CMV-specific CD8⁺ T cell response and CMV clearance in the recipient. Currently, a phase I/II clinical study (LUMC 2004-01) on the treatment of refractory CMV reactivation using CMV pp65-specific CD8⁺ T cells is performed at the department of Hematology at the Leiden University Medical Center (LUMC). In the good manufacturing practice (GMP) facility of the LUMC (IGFL) CMV pp65-specific CD8⁺ T cells are generated by stimulating donor- or patient-derived peripheral blood mononuclear cells (PBMC) with a CMV pp65-derived human leukocyte antigen (HLA)-A02- and/or HLA-B07-restricted peptide. After stimulation CD8⁺ T cells specific for these peptides will start to produce Interferon-gamma (IFN γ) and the specific CD8⁺ T cells can be isolated based on this IFN γ production. After isolation, the T cells are cultured for 7 -14 days, after which they are adoptively transferred to patients. Since the introduction of protocol LUMC 2004-01, sixteen CMV pp65-specific CD8⁺ T cell lines have been generated. Of those T cell lines, eight have been infused in six patients without any side effects. All treated patients cleared the CMV within weeks after infusion. Isolation of CMV pp65-specific T cells from a donor using this protocol is only possible when the donor is CMV seropositive. Due to the HLA restriction (HLA-A02 or HLA-B07) and the time frame needed for the generation of the CMV-specific CD8⁺ T cell line, this treatment regimen could not be applied to all patients. Furthermore, only CMV-specific CD8⁺ T cells were generated, while clinical observations have indicated that CMV-specific CD4⁺ T cells may promote development and persistence of a CMV-specific CD8⁺ T cell response in-vivo. Therefore, to increase the potential clinical use of CMV-specific T cells and to increase the in-vivo potential of the CMV-specific T cells we will start a new clinical protocol, in which we will use a CMV pp65 protein-spanning peptide pool of 15-mer peptides for the simultaneous generation of donor- derived CMV pp65-specific CD8⁺ and CD4⁺ T cell product. Using this peptide pool both CMV pp65-specific CD4⁺ and CD8⁺ T cells can be isolated irrespective of HLA typing of the donor. Secondly, the isolated CMV pp65-specific T cells will be directly administered after isolation to decrease the level of manipulation of these T cells and to shorten the period between

the onset of CMV disease and the infusion of the CMV-specific cells allowing more accurate therapeutic intervention.

2. OBJECTIVES

- To assess the feasibility, tolerability and safety of administration of donor derived CMV pp65-specific T cells in patients with CMV reactivation or CMV disease after alloSCT.
- To determine the presence of CMV-specific T cells at different time points after infusion of CMV pp65-specific T cells.
- To evaluate whether administration of CMV pp65-specific T cells in patients with persistent CMV reactivation or CMV disease after alloSCT leads to complete or partial responses.

3. STUDY DESIGN

[figure not shown]
This is an open-label non-randomized phase I/II feasibility study to treat patients with persistent CMV reactivation or CMV disease after alloSCT with administration of CMV pp65-specific T cells generated by use of a CMV pp65 protein-spanning peptide pool.

Patients who receive an alloSCT from a CMV-positive donor are monitored weekly for CMV reactivation using PCR for the detection of CMV DNA. In case of CMV reactivation (defined as CMV DNA load >1000 cp/ml) patients will be treated with antiviral therapy consisting of valganciclovir, ganciclovir or foscarnet.

For patients with CMV reactivation who fail antiviral therapy (defined as **CMV reactivation treatment failure**: persistent CMV DNA load of more than 1000 cp/ml or CMV disease after 2 weeks of adequate treatment with antiviral therapy or relapse of CMV DNA load of more than 1000 cp/ml within 4 weeks after adequate treatment with antiviral therapy or contraindication for treatment with antiviral therapy at the discretion of the physician) or develop CMV disease (organ dysfunction (pneumonitis, enteritis, retinitis, encephalitis, hepatitis, and bone marrow suppression) due to CMV infection), CMV pp65-specific CD4+ and CD8+ T cells will be generated from donor PBMC by overnight in vitro stimulation with pp65 CMV peptide pools. CMV-specific CD4+ and CD8+ T cells will be isolated based on their IFN γ production and administered to the patient directly after quality control. If alloSCT was performed using CD34 positive cell selection and the CD34 negative subfraction has been cryopreserved at a GMP facility, this fraction can also be used for selection of CMV-specific T cells. Antiviral therapy will be continued after infusion of CMV pp65-specific T cells according to standard antiviral treatment protocols at the discretion of the physician.

In case of ongoing CMV reactivation or CMV disease the infusion of CMV pp65-specific T cells may be repeated 2 times with at least 4 weeks interval. The patient will be monitored for adverse events and for effect on CMV DNA load. Follow-up of patients will be performed until 6 months after infusion of CMV pp65-specific T cells or until subsequent DLI, whichever comes first.

Study design for treatment of CMV reactivation and/or CMV disease with allogeneic CMV pp65-specific T cells.

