6.5 Description and justification of route of administration and dosage

The CMV pp65-specific T cells will be administered intravenously. The aimed dose of CMV pp65-specific T cells of $10\text{-}20 \times 10^6$ total T cells is based on the amount of cells we expect to isolate on the basis of the currently performed phase I/II clinical study (LUMC 2004-01) on the treatment of refractory CMV reactivation using CMV pp65-specific CD8+ T cells and preclinical data of the current strategy. All cells isolated will be infused to maximize the effect if $\geq 20\%$ of the T cells are IFN γ and/or CD137 positive and the maximal amount of non-specific T cells in the product is $< 0.3 \times 10^6$ /kg body weight in patients transplanted with related donors and $< 0.15 \times 10^6$ /kg body weight in case of unrelated donors. The maximal amount of non-specific T cells administered in the T cell product is based on the current protocol for unselected DLI at 3 months in which comparable numbers of unselected CD3 positive cells are administered with acceptable toxicity. If the number of number of non-specific T cells in the product exceeds these criteria, the infused dose will be adjusted accordingly.

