7. METHODS

7.1 Study endpoints

- The number of events of acute GvHD, death and all other adverse events.
- The number of CMV-specific T cells at different time points after infusion of CMV pp65-specific T cells.
- The number of complete responses or partial responses of CMV reactivation or CMV disease after infusion of CMV pp65-specific T cells.

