7.6 End of study

End of the study is defined as 6 months after the infusion of CMV pp65-specific T cells of patient number 15 or at time of subsequent DLI of patient number 15.

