9.4 Statistical analysis

Descriptive statistics and univariate and multivariate analysis will be used to characterize the study population. The endpoint of analysis of treatment toxicity will be done primarily by tabulation of the incidence of side effects with CTCAE grade 2 or more (see Appendix B) or acute GvHD overall grade III or more (see Appendix C). Actuarial competing risk estimates of probability of death will be split by cause of death where a difference will be made between death due to CMV disease and death due to side effects of the treatment. The endpoints of presence of CMV-specific T cells and number of complete remissions and partial remissions of CMV reactivation or CMV disease after administration of CMV pp65-specific T cells will be documented.

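### Follow-up for death stops at donor lymphocyte infusion (DLI), so deaths after DLI within the 6-month window are not systematically collected, although death is an endpoint with a planned competing-risk estimate

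*Protocol*

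**What the plan says.** Section 3 of the protocol runs patient follow-up "until 6 months after infusion of CMV pp65-specific T cells or until subsequent DLI, whichever comes first". The summary gives the same stop but starts the clock differently: "until 6 months after last infusion of CMV pp65-specific T cells or until subsequent DLI, whichever comes first". Section 7.6 lets the study itself close 6 months after patient 15's infusion "or at time of subsequent DLI of patient number 15", and 11.3 repeats this.

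The first-listed endpoint in 7.1 is "The number of events of acute GvHD, death and all other adverse events". Section 9.4 plans "Actuarial competing risk estimates of probability of death", divided by cause so that "a difference will be made between death due to CMV disease and death due to side effects of the treatment".

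DLI appears in two further places. Section 5.3 stores unused donor cells for later unselected DLI. Section 6.5 justifies the limit on non-specific T cells by reference to the "current protocol for unselected DLI at 3 months".

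**The concern.** Stopping at DLI makes sense for attributing acute GvHD, because DLI can itself cause it. The stop is written for the whole of follow-up, however, so it also ends the recording of survival. A patient who receives DLI and then dies within 6 months of infusion may not appear as a death, although death is an endpoint and its probability is to be estimated over time.

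An actuarial method would treat such a patient as censored at DLI. That is harmless only if patients given DLI have the same later risk of death as those still followed. If DLI goes to patients who are doing badly, censoring understates mortality. If it goes to patients well enough to receive it, censoring overstates mortality. At stake is whether the 6-month death probability and its split by cause describe all infused patients or only their time before DLI.

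**Working it through.** **1. What is collected after DLI.** The schedules in 7.2.3 (adults) and 7.2.4 (children) lie inside the follow-up that section 3 ends at DLI. No section adds a visit or a survival enquiry afterwards. Two sections reach a little further. Section 8.3 follows adverse events until they resolve or stabilise, with no DLI cut-off. Section 8.2 gives no end date for reporting serious events. A death from an event already open at DLI, or one that happens to be reported, could therefore be recorded. A new death after DLI has no systematic route into the data.

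**2. The plan's own figures.** The documents give no DLI rate, no reason for DLI and no expected mortality, so there is no figure to reproduce on this point. The only design figure is 15 patients, which rests on response (9.3). With one-sided alpha 0.05, power 90%, p0 = 0.30 and p1 = 0.66:

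n = [(1.645·√(0.30·0.70) + 1.282·√(0.66·0.34)) / 0.36]² = 14.29, rounded up to 15.

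This reproduces and is not affected by the point.

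**3. Loss of information on death.** The number of patients given DLI before 6 months, k, is an assumption: 5, with 2 and 8 as the range. If no treatment-related death is seen among n patients with complete follow-up, the exact two-sided 95% upper limit is 1 − 0.025^(1/n).

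| k (assumed) | n = 15 − k | Upper limit for 0/n |
|---|---|---|
| 0 | 15 | 21.8% |
| 2 | 13 | 24.7% |
| 5 | 10 | 30.8% |
| 8 | 7 | 41.0% |

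These limits treat patients given DLI as contributing nothing, so for each k they bound the loss from above. An actuarial estimate uses the time before DLI. If the 5 patients contribute on average half of their follow-up at a constant hazard (assumption), the effective n is 10 + 5 × 0.5 = 12.5, and the limit is 1 − 0.025^(1/12.5) = 25.6%. For k = 5 the loss is then about 4 percentage points instead of 9.

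**4. Room for bias.** Each patient whose 6-month status is unknown is 1/15 = 6.7% of the trial. With no assumption about outcomes after DLI, the crude 6-month death proportion is uncertain by k/15: 13 points for k = 2, 33 for k = 5 and 53 for k = 8. These are worst-case widths, not expected bias, and they give no direction.

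**5. Deaths from other causes.** Nine of the 12 adult indications in Appendix D are haematological malignancies, so relapse deaths are possible. Suppose constant hazards, with a 6-month net risk of 10% each for CMV death and treatment death (assumption). Each hazard is −ln 0.9 = 0.1054. If relapse deaths were censored, the CMV-death estimate would be ½ × (1 − 0.9²) = 0.0950. If they are counted as a competing event with hazard λr = −ln(1 − r), the cumulative incidence is (0.1054/Λ)(1 − e^(−Λ)), where Λ = 0.2107 + λr. This gives 0.0903, 0.0855 and 0.0804 for r = 10%, 20% and 30%. Censoring would therefore overstate CMV death by 0.5 to 1.5 percentage points.

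**The case against.** **Stopping at DLI is coherent.** Unselected DLI supplies more donor T cells, and by 6.2 the blood of CMV-infected people contains CMV-specific T cells. DLI therefore confounds CMV DNA and T-cell counts as well as GvHD. This stands. A reader might infer that CMV DNA and response should also be followed past DLI, but that is a debatable choice of what to estimate, and the protocol's cut-off for those endpoints is defensible. The argument does not extend to whether a patient is alive.

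**Section 9.4 does not list every cause of death.** A reader might infer that relapse deaths have no place in the estimate and must be censored or misassigned. The text does not support this. It requires two causes to be told apart and says neither that they are the only causes nor that other deaths are censored. A further competing category is a natural reading, and the full list may properly sit in the analysis plan. Even if such deaths were censored, the error in step 5 is small.

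**Informative timing of DLI is not documented.** This also stands. The 3-month reference in 6.5 could describe a scheduled DLI, and it is cited there only to justify a cell limit. Neither 5.3 nor 6.5 says how many trial patients will receive DLI, or when.

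**Deaths after DLI are not wholly invisible.** Correct, given 8.2 and 8.3. The claim is only that they are not systematically collected.

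**No decision rule uses the death probability.** Sample size rests on response and the pause rule in 7.5 on acute GvHD. This limits the consequence but does not remove it, because death remains a stated endpoint.

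**Conclusion.** The point holds for survival. The protocol ends all scheduled follow-up at DLI, names death in its first-listed endpoint and plans an actuarial estimate of it, so new deaths after DLI within 6 months can be missed. This is a rule about what data are collected, and an analysis plan cannot repair it afterwards.

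The loss of information follows from the text for any patient given DLI before 6 months. Bias is possible but not shown: it needs DLI timing to be related to prognosis, which is an inference, and its direction is unknown. The size depends on an undocumented number of DLIs. Under an assumed 5 of 15, the move from a 22% to a 31% upper limit is an upper bound, and about 26% is more realistic if those patients contribute half of their follow-up. If few patients receive DLI, the effect is small. The point deserves correction because the remedy is cheap, but it does not undermine the sample size or the pause rule.

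**What to change.** - **Section 3 and summary:** keep DLI as the cut-off for GvHD attribution and for the CMV response and T-cell endpoints. Add that vital status and cause of death are recorded for every infused patient to 6 months after the last infusion, regardless of DLI.
- **Start of the clock:** section 3 counts from infusion and the summary from the last infusion. Reconcile them; the wording above uses the last infusion.
- **Deaths after DLI:** flag and list them separately, including GvHD deaths after DLI, so that they are not automatically charged to the study product.
- **Section 9.4:** state that deaths from relapse or other causes count as a further competing event and are not censored.
- **Sections 7.6 and 11.3:** align the end of study, so that patient 15's DLI does not close survival recording early.

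The cost is a few sentences and a check of routine records for patients given DLI. The decision to give DLI, and patient care, are untouched. The drawback is that the cause of some deaths after DLI will be ambiguous; the separate flag makes that visible but does not resolve it.
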